--

[figure not shown]
	
The first visit and first dosing for the open-label extension phase of the study will occur immediately on the day of the last visit of the double-blind period or up to 1 week following the double-blind period. Day 1 of the open-label extension period will be defined as the day of administration of the first dose of difelikefalin in the open-label extension period and will occur preferably on the first dialysis session of the first treatment week (i.e., Monday for subjects on a Monday-Wednesday-Friday dialysis schedule, or Tuesday for subjects on a Tuesday-Thursday-Saturday dialysis schedule).
 
The last dose of open-label difelikefalin will be administered at the last dialysis visit on Week 14, or early termination.
 
Subjects will complete the Skindex-10 scale and 5-D itch scale at Week 4, Week 8, Week 12 and at the end-of-treatment visit, which corresponds to the first dialysis visit following the last dose of difelikefalin given in the open-label extension (i.e., first dialysis on Week 15).
 
Blood samples for clinical laboratory tests will be collected at the end of treatment or early termination visit; in addition, blood samples for analysis of serum potassium will be collected every 2 weeks (on dialysis days), i.e., at Week 2, Week 4, Week 6, Week 8, Week 10 and Week 12 of the open-label extension. Vital signs will be monitored on Day 1, at Week 4, Week 8, Week 12 and at the end of treatment or early termination visit. AEs and concomitant medications will be continuously recorded throughout the open-label treatment period.
 
12-lead ECGs will be monitored at the open-label end of treatment or early termination visit.
 
Follow-up Period
 
A final safety follow-up visit will be conducted in 7 to 10 days:
 
 • After the end-of-treatment visit of the double-blind period for subjects not participating in the open-label extension phase • After the end-of-treatment visit of the open-label extension period for subjects participating in the open-label extension phase • Or after the early termination visit during either the double-blind period or the open-label extension phase

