4.8.2 Clinical Laboratory Evaluations

Subject clinical laboratory evaluations including serum chemistry, haematology and potassium will be summarized descriptively using central laboratory.

Laboratory values will be reported in units according to the International System of Units as per [Appendix 2](#) in the SAP.

Summaries of actual values and the change from baseline to each time point (when applicable) including last post-baseline measurement will be presented for quantitative laboratory parameters. Descriptive statistics are calculated by treatment sequence and all sequences pooled on both the actual values and the change from baseline.

Baseline is defined as the last measurement taken on or prior to the first day of open-label dosing. This will typically be the end of treatment visit for the double-blind period.

Laboratory test results will be classified according to whether the value was below (L), within (N), or above (H) the laboratory parameter reference range. A summary of shifts will compare the baseline L/N/H classification for each laboratory test to the L/N/H classification at end of open-label extension period and at last post-baseline. For serum potassium, shift table comparing the baseline L/N/H classification to each post baseline L/N/H classification (including last post-baseline) will also be provided.

All laboratory results will be listed, including data at any unscheduled visits. In addition, all abnormal (with classification of L or H) laboratory values will be presented in a separate listing.

4.8.3 12-lead Electrocardiogram (ECG) Evaluations

Summary tables for 12-lead ECG include descriptive statistics for baseline and each post baseline assessment including last post-baseline measurement during the open-label extension period. Descriptive statistics are calculated by treatment sequence and all sequences pooled on both the actual values and the change from baseline for Heart Rate, QT interval, QTcF interval, QTcB interval, RR interval, P-wave, QRS complex duration and PR interval. Overall interpretation of the 12-lead ECG readings is to be tabulated as well by treatment sequence and all sequences pooled at baseline, at end of open-label extension period and at last post-baseline assessment.

Baseline is defined as the last measurement taken on or prior to the first day of open-label dosing. This will typically be the end of treatment visit for the double-blind period.

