All 12-lead ECG data will be listed in a by-subject listing and will be sorted by subject identifier and date of assessment.

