14.3.4.2	Listing of Abnormal Laboratory Values during the Open-label Extension Period: Haematology: Serum Chemistry	Open-label Safety Analysis Set
14.3.5.1	Clinical Laboratories - Haematology: Absolute Values and Changes from Baseline during the Open-label Extension Period	Open-label Safety Analysis Set
14.3.5.2	Clinical Laboratories - Chemistry: Absolute Values and Changes from Baseline during the Open-label Extension Period	Open-label Safety Analysis Set
14.3.5.3	Clinical Laboratories - Chemistry Potassium: Absolute Values and Changes from Baseline during the Open-label Extension Period	Open-label Safety Analysis Set
14.3.5.4	Clinical Laboratories - Haematology: Shifts from Baseline to the End of Open-label Extension Period by L/N/H Classification	Open-label Safety Analysis Set
14.3.5.5	Clinical Laboratories – Chemistry: Shifts from Baseline to the End of Open-label Extension Period by L/N/H Classification	Open-label Safety Analysis Set
14.3.5.6	Clinical Laboratories – Chemistry Potassium: Shifts from Baseline to the End of Open-label Extension Period by L/N/H Classification	Open-label Safety Analysis Set
14.3.6.1	ECG: Absolute Values and Changes from Baseline during the Open-label Extension Period	Open-label Safety Analysis Set
14.3.6.2	ECG: Overall Interpretation during the Open-label Extension Period	Open-label Safety Analysis Set
14.3.7.1	Vital Signs: Absolute Values and Changes from Baseline during the Open-label Extension Period	Open-label Safety Analysis Set
14.3.8.1	Concomitant Medication by ATC Level 2 and ATC Level 4 - Open-label Extension Period	Open-label Safety Analysis Set
14.3.8.2	Concomitant Antipruritic Medication by Ingredient - Open-label Extension Period	Open-label Safety Analysis Set

Figures

	Titles	Population
14.2.1.1	LS Mean Change from Baseline in Total 5-D Itch Score by Week during the Open-label Extension Period – Line Plot	Open-label Safety Analysis Set
14.2.1.2	LS Mean Change from Baseline in Total 5-D Itch Score by Week during Overall Study – Line Plot	Open-label Safety Analysis Set
14.2.1.3	LS Mean Change from Baseline in Total 5-D Itch Score as well as each Domain Score by Week during the Open-label Extension Period – Bar Chart	Open-label Safety Analysis Set
14.2.1.4	LS Mean Change from Baseline in Total 5-D Itch Score as well as each Domain Score by Week during Overall Study – Bar Chart	Open-label Safety Analysis Set

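### SAP 4.8.3 counts ECG interpretation separately at each time point and plans no within-subject shift, so no summary table shows how many subjects went from normal to abnormal

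*SAP*

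**What the plan says.** SAP 4.8.3 provides two summaries of the open-label ECGs. The first is descriptive statistics of values and changes from baseline for heart rate, the intervals and the waves. The second concerns the reader's verdict: "Overall interpretation of the 12-lead ECG readings is to be tabulated as well by treatment sequence and all sequences pooled at baseline", followed by the two later time points, "at end of open-label extension period and at last post-baseline assessment". The matching entry in SAP Appendix 1 is Table 14.3.6.2, "ECG: Overall Interpretation during the Open-label Extension Period".

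Laboratory results are treated differently. SAP 4.8.2 states: "A summary of shifts will compare the baseline L/N/H classification for each laboratory test to the L/N/H classification at end of open-label extension period", and adds last post-baseline. Tables 14.3.5.4 to 14.3.5.6 carry this into Appendix 1, for example "Clinical Laboratories - Haematology: Shifts from Baseline to the End of Open-label Extension Period by L/N/H Classification".

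Three other provisions bear on the point:

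- **Schedule.** The protocol synopsis says "12-lead ECGs will be monitored at the open-label end of treatment or early termination visit". Protocol Table 2 shows no other open-label ECG.
- **Baseline.** SAP 4.8.3 takes the last ECG on or before the first open-label dosing day, and notes that this is typically the end-of-treatment reading of the double-blind period.
- **Listings.** SAP 4.8.3 adds: "All 12-lead ECG data will be listed in a by-subject listing and will be sorted by subject identifier and date of assessment". Listing 16.2.9.2 is set aside for the qualitative assessment.

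**The concern.** ECG is a named safety endpoint (SAP 2.6.4), and the extension has no concurrent control. The natural question for the interpretation data is how many subjects with a normal ECG at entry had an abnormal one afterwards. Counts at separate times cannot answer it, because subjects who become abnormal are offset by subjects who become normal.

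The counts may also rest on different subjects. A subject with a baseline ECG and no later one appears in the first column only, and SAP 4.1.1 leaves missing values out of percentages unless otherwise specified.

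The question matters most in the Placebo/Difelikefalin sequence. There the baseline ECG typically precedes any difelikefalin, so the change in interpretation is before-and-after evidence on first exposure.

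**Working it through.** The plan states no figure for this item, so there is none to reproduce. The check has four steps.

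**1. Laboratory and ECG plans side by side**

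| | Laboratory tests | ECG interpretation |
|---|---|---|
| SAP text | 4.8.2: shift from baseline to end of period and to last post-baseline | 4.8.3: tabulation at three time points |
| Summary tables | 14.3.5.4 to 14.3.5.6, titled as shifts | 14.3.6.2, no shift in the title |
| Listing of abnormal values only | 14.3.4.1 and 14.3.4.2 | none |
| Full by-subject listing | yes | yes, 16.2.9.2 |

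The SAP uses the word shift where it wants one, and does not use it for ECG.

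**2. What separate counts determine**

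Take N subjects with both readings, a abnormal at baseline and b abnormal afterwards. Let x be the number going from normal to abnormal. The b later abnormals consist of x plus those abnormal at both times, and the latter number at most a. So x is at least b − a. Also x cannot exceed b, nor the N − a subjects who started normal:

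max(0, b − a) ≤ x ≤ min(b, N − a)

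The documents give neither the number entering the extension nor an abnormal rate. All inputs below are therefore assumed. The value 258 is the planned enrolment in SAP 2.4 and serves as a ceiling.

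| N | a | b | smallest x | largest x |
|---|---|---|---|---|
| 200 | 20 | 20 | 0 | min(20, 180) = 20 |
| 200 | 60 | 60 | 0 | min(60, 140) = 60 |
| 200 | 60 | 70 | 70 − 60 = 10 | min(70, 140) = 70 |
| 200 | 80 | 80 | 0 | min(80, 120) = 80 |
| 258 | 77 | 77 | 0 | min(77, 181) = 77 |

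In a shift table x is one cell and is known exactly.

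**3. Whether the third time point helps**

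Only one open-label ECG is scheduled. In SAP Table 3 the Open-label Week 14 window opens on Day 92, and SAP 4.1.3 maps early-termination visits to the window they fall in. For a subject whose ECG lies in the Week 14 window, end of period and last post-baseline are normally the same reading. For a subject who stops earlier, reading end of period as the Week 14 label, only last post-baseline captures the ECG. The third column therefore covers early terminators, but it is still a separate count and step 2 applies to it.

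**4. Whether another planned output gives x**

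- **Quantitative ECG table (14.3.6.1).** It summarises paired changes in the ECG parameters, with minimum and maximum under SAP 4.1.1. It does not cover the interpretation category.
- **Adverse events.** Protocol 9.3 makes a new or worsened ECG finding an adverse event if the investigator considers it clinically relevant. Other changes are not captured, and no table groups ECG findings.
- **Listing 16.2.9.2.** It would allow a hand count if it shows both readings. It is titled for the open-label period, and SAP 4.1.5 says listings show open-label data and derived variables. The baseline reading typically belongs to the double-blind end-of-treatment visit, and the SAP does not say that the listing includes it.

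**The case against.** The case for leaving the plan alone is fair in several respects.

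- **The data are not lost.** A reader might infer that the number of newly abnormal subjects cannot be recovered at all. The documents do not support that: a by-subject listing is planned, and clinically relevant new findings must be reported as adverse events. What stands is that no summary table gives the number, and that the listing's coverage of the baseline ECG is unstated.
- **Within-subject ECG change is already analysed.** This is true for heart rate, the intervals and the waves, including both QTc corrections, and extreme changes show as minimum and maximum. The gap concerns the interpretation category only.
- **Interpretation is itself the investigator's judgement.** Protocol 9.3 has the sites read the ECGs, so a shift table is no more objective than adverse event reporting. It would, however, include changes not judged clinically relevant and gather them in one place.
- **The protocol does not ask for a shift.** Protocol 12.9.4 requires baseline and change in ECG parameters, and the SAP already goes further. There is no conflict between the documents.
- **The shells are not available.** SAP 4.1.1 leaves details of categorical tables to shells outside these documents. A cross-tabulation there cannot be ruled out, but the SAP does not commit to one.
- **A shift would not isolate a drug effect in everyone.** In the Difelikefalin/Difelikefalin sequence the baseline is typically taken after 12 weeks of active treatment, so a pooled line mixes two kinds of baseline. This governs how the table is read and is not a reason to omit it.

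**Conclusion.** The point holds as a minor reporting gap. As specified, SAP 4.8.3 and Table 14.3.6.2 give separate counts, and no planned summary table gives the number of subjects whose ECG interpretation moved from normal to abnormal. The SAP already has the better format, in its laboratory shift tables.

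A reader might take the ranges above as a sign that dozens of new abnormalities could go unnoticed. The documents do not support that. The upper limit with 80 of 200 abnormal at both times requires all 80 baseline abnormalities to resolve while 80 other subjects become abnormal. The ranges are algebraic limits on assumed rates and numbers, and show only that the table does not identify the count.

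The conclusion rests on the SAP text and table titles, since neither the shells nor the interpretation categories are shown. The analysis is descriptive, so alpha, power and every estimate are unaffected. The separate SAP for the double-blind period is not among the documents, and nothing is claimed about it.

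**What to change.** 1. In SAP 4.8.3 and Appendix 1, make Table 14.3.6.2 a shift table of baseline interpretation against last post-baseline interpretation, and also against end of period, by treatment sequence and pooled. Include a missing category on both axes.
2. Add a line for newly abnormal subjects, with the denominator restricted to subjects who have both ECGs. State which interpretation categories count as abnormal.
3. State that the Placebo/Difelikefalin sequence carries the before-and-after evidence on first exposure, and that the Difelikefalin/Difelikefalin baseline is typically already on drug.
4. State that Listing 16.2.9.2 includes the baseline ECG.

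The cost is one changed shell and a few sentences. All the data are already collected and the format follows Tables 14.3.5.4 to 14.3.5.6. The separate counts remain available as the margins of the new table, so nothing is lost.

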4.8.4 Vital Signs Evaluations

Summary tables for vital signs include descriptive statistics for baseline and each post baseline assessment including last post-baseline measurement. Descriptive statistics are calculated by treatment sequence and all sequences pooled on both the actual values and the change from baseline for Body Temperature, Sitting Respiratory Rate, Sitting Radial Pulse Rate, Sitting Systolic Blood Pressure and Sitting Diastolic Blood Pressure.

Baseline is defined as the last measurement taken on or prior to the first day of open-label dosing. This will typically be Day 1 of the open-label extension period (prior to treatment).

All vital signs will be listed in a by-subject listing and will be sorted by subject identifier and date of assessment.

4.8.5 Other Measures

Special situations during the open-label extension period will be presented in a frequency table displaying all special situations types as per section 10.8.1 of the protocol by treatment sequence and all sequences pooled. The

special situations will be reported on a per-subject basis, i.e., this means a subject will contribute only once to the count for a given special situation category.

All special situations will be coded using MedDRA (when applicable). Coded special situations will be summarized by Primary System Organ Class and Preferred Term by treatment sequence and all sequences pooled for open-label extension period. In addition, all information regarding special situations will be listed.

In case there are 10 or less special situations in total, then special situations will be listed only.

4.9 Physical Examinations

Not applicable as physical examination finding will be recorded through medical history or AEs if clinically relevant.

4.10 Other Analyses

Pregnancy test results will be listed only.

REFERENCES

1. Guidance on Statistical Principles for Clinical Trials in Pharmaceutical Development. China Food and Drug Administration, P. R. China; Jun 2016.
2. Statistical Principles for Clinical Trials. ICH Harmonised Guideline; September 1998.

APPENDICES

Appendix 1: List of TFLs

Tables

Output No.	Titles	Population
14.1.1.1	Subject Disposition - Open-label Extension Period	Open-label Safety Analysis Set
14.1.2.1	Important Protocol Deviations - All Study Periods	Full Analysis Set
14.1.2.2	Non-Important Protocol Deviations - All Study Periods	Full Analysis Set
14.1.3.1	Demographics and Baseline Characteristics	Open-label Safety Analysis Set
14.1.3.2	Baseline Disease Characteristics	Open-label Safety Analysis Set
14.1.4.1	Medical History Recorded by System Organ Class and Preferred Term	Open-label Safety Analysis Set
14.1.5.1	Prior Medication by ATC Level 2 and ATC Level 4	Open-label Safety Analysis Set
14.1.5.2	Prior Antipruritic Medications by Ingredient	Open-label Safety Analysis Set
14.1.6.1	Study Drug Administration and Treatment Compliance - Open-label Extension Period	Open-label Safety Analysis Set
14.1.7.1	Dialysis Administration - Open-label Extension Period	Open-label Safety Analysis Set
14.2.1.1	MMRM Analysis of Change from Baseline in Total 5-D Itch Score as well as each Domain Score by Week during Open-label Extension Period (No Imputation)	Open-label Safety Analysis Set
14.2.1.2	MMRM Analysis of Change from Baseline in Total 5-D Itch Score as well as each Domain Score by Week during Overall Study (No Imputation)	Open-label Safety Analysis Set
14.2.2.1	Subjects with \geq 5-point Improvement from Baseline in Total 5-D Itch Score by Week during Overall Study	Open-label Safety Analysis Set
14.2.3.1	MMRM Analysis of Change from Baseline in Total Skindex-10 Scale Score as well as each Domain Score by Week during Open-label Extension Period (No Imputation)	Open-label Safety Analysis Set
14.2.3.2	MMRM Analysis of Change from Baseline in Total Skindex-10 Scale Score as well as each Domain Score by Week during Overall Study (No Imputation)	Open-label Safety Analysis Set
14.2.4.1	Subjects with \geq 15-point Improvement from Baseline in Total Skindex-10 Scale Score by Week during Overall Study	Open-label Safety Analysis Set
14.3.1.1	Overall Summary of Adverse Events during Open-label Extension Period	Open-label Safety Analysis Set
14.3.1.2	Adverse Events during Open-label Extension Period by System Organ Class and Preferred Term	Open-label Safety Analysis Set
14.3.1.3	Serious Adverse Events during Open-label Extension Period by System Organ Class and Preferred Term	Open-label Safety Analysis Set
14.3.1.4	Related Adverse Events during Open-label Extension Period by System Organ Class and Preferred Term	Open-label Safety Analysis Set
14.3.1.5	Related Serious Adverse Events during Open-label Extension Period by System Organ Class and Preferred Term	Open-label Safety Analysis Set
14.3.1.6	Adverse Events Leading to Study Drug Discontinuation during the Open-label Extension Period by System Organ Class and Preferred Term	Open-label Safety Analysis Set
14.3.1.7	Related Adverse Events Leading to Study Drug Discontinuation during the Open-label Extension Period by System Organ Class and Preferred Term	Open-label Safety Analysis Set

Output No.	Titles	Population
14.3.1.8	Adverse Events during Open-label Extension Period by System Organ Class, Preferred Term, and Maximum Severity	Open-label Safety Analysis Set
14.3.1.9	Adverse Events during the Open-label Extension Period by System Organ Class, Preferred Term, and Strongest Relationship	Open-label Safety Analysis Set
14.3.1.10	Adverse Events of Special Interest during Open-label Extension Period by Preferred Term	Open-label Safety Analysis Set
14.3.1.11	Related Adverse Events of Special Interest during Open-label Extension Period by Preferred Term	Open-label Safety Analysis Set
14.3.1.12	Most common Adverse Events ($\geq 2\%$ or more of subjects in any treatment sequence) during the Open-label Extension Period by Preferred Term	Open-label Safety Analysis Set
14.3.1.13	Special Situations during Open-label Extension Period by Category	Open-label Safety Analysis Set
14.3.1.14	Special Situations during Open-label Extension Period by System Organ Class and Preferred Term	Open-label Safety Analysis Set
14.3.2.1	Serious Adverse Events during the Open-label Extension Period	Open-label Safety Analysis Set
14.3.2.2	Adverse Events Leading to Deaths during the Open-label Extension Period	Open-label Safety Analysis Set
14.3.2.3	Adverse Events Leading to Study Drug Discontinuation during the Open-label Extension Period	Open-label Safety Analysis Set
14.3.2.4	Adverse Events Leading to Early Study Termination during the Open-label Extension Period	Open-label Safety Analysis Set
14.3.2.5	Adverse Events of Special Interest during the Open-label Extension Period	Open-label Safety Analysis Set
14.3.4.1	Listing of Abnormal Laboratory Values during the Open-label Extension Period: Haematology: Haematology	Open-label Safety Analysis Set
14.3.4.2	Listing of Abnormal Laboratory Values during the Open-label Extension Period: Haematology: Serum Chemistry	Open-label Safety Analysis Set
14.3.5.1	Clinical Laboratories - Haematology: Absolute Values and Changes from Baseline during the Open-label Extension Period	Open-label Safety Analysis Set
14.3.5.2	Clinical Laboratories - Chemistry: Absolute Values and Changes from Baseline during the Open-label Extension Period	Open-label Safety Analysis Set
14.3.5.3	Clinical Laboratories - Chemistry Potassium: Absolute Values and Changes from Baseline during the Open-label Extension Period	Open-label Safety Analysis Set
14.3.5.4	Clinical Laboratories - Haematology: Shifts from Baseline to the End of Open-label Extension Period by L/N/H Classification	Open-label Safety Analysis Set
14.3.5.5	Clinical Laboratories – Chemistry: Shifts from Baseline to the End of Open-label Extension Period by L/N/H Classification	Open-label Safety Analysis Set
14.3.5.6	Clinical Laboratories – Chemistry Potassium: Shifts from Baseline to the End of Open-label Extension Period by L/N/H Classification	Open-label Safety Analysis Set
14.3.6.1	ECG: Absolute Values and Changes from Baseline during the Open-label Extension Period	Open-label Safety Analysis Set
14.3.6.2	ECG: Overall Interpretation during the Open-label Extension Period	Open-label Safety Analysis Set
14.3.7.1	Vital Signs: Absolute Values and Changes from Baseline during the Open-label Extension Period	Open-label Safety Analysis Set
14.3.8.1	Concomitant Medication by ATC Level 2 and ATC Level 4 - Open-label Extension Period	Open-label Safety Analysis Set
14.3.8.2	Concomitant Antipruritic Medication by Ingredient - Open-label Extension Period	Open-label Safety Analysis Set

Figures

	Titles	Population
14.2.1.1	LS Mean Change from Baseline in Total 5-D Itch Score by Week during the Open-label Extension Period – Line Plot	Open-label Safety Analysis Set
14.2.1.2	LS Mean Change from Baseline in Total 5-D Itch Score by Week during Overall Study – Line Plot	Open-label Safety Analysis Set
14.2.1.3	LS Mean Change from Baseline in Total 5-D Itch Score as well as each Domain Score by Week during the Open-label Extension Period – Bar Chart	Open-label Safety Analysis Set
14.2.1.4	LS Mean Change from Baseline in Total 5-D Itch Score as well as each Domain Score by Week during Overall Study – Bar Chart	Open-label Safety Analysis Set
14.2.1.5	Percentage of Subjects with ≥ 5 -point Improvement from Baseline in Total 5-D Itch Score by Week during Open-label Extension Period – Bar Chart	Open-label Safety Analysis Set
14.2.2.1	LS Mean Change from Baseline in Total Skindex-10 Scale Score by Week during the Open-label Extension Period – Line Plot	Open-label Safety Analysis Set
14.2.2.2	LS Mean Change from Baseline in Total Skindex-10 Scale Score by Week during Overall Study – Line Plot	Open-label Safety Analysis Set
14.2.2.3	LS Mean Change from Baseline in Total Skindex-10 Scale Score as well as each Domain Score by Week during Open-label Extension Period – Bar Chart	Open-label Safety Analysis Set
14.2.2.4	LS Mean Change from Baseline in Total Skindex-10 Scale Score as well as each Domain Score by Week during Overall Study – Bar Chart	Open-label Safety Analysis Set
14.2.2.5	Percentage of Subjects with ≥ 15 -point Improvement from Baseline in Total Skindex-10 Scale Score by Week during Overall Study – Bar Chart	Open-label Safety Analysis Set

Listings

	Titles	Population
16.2.1.1	Subject Disposition	Open-label Safety Analysis Set
16.2.1.2	Inclusion Criteria not Met/Exclusion Criteria Met - Open-label Extension Period	All Subjects Entered Open-label Extension Period
16.2.2.1	Protocol Non-Compliance - All Study Periods	Full Analysis Set
16.2.4.1	Demographic Data	Open-label Safety Analysis Set
16.2.4.2	Baseline Disease Characteristic	Open-label Safety Analysis Set
16.2.4.3	Medical History	Open-label Safety Analysis Set
16.2.4.4	Prior and Concomitant Medications	Open-label Safety Analysis Set
16.2.4.5	Prior and Concomitant Procedures	Open-label Safety Analysis Set
16.2.5.1	Study Drug Administration Data - Open-label Extension Period	Open-label Safety Analysis Set
16.2.5.2	Study Drug Exposure, Dialysis and Compliance - Open-label Extension Period	Open-label Safety Analysis Set
16.2.5.3	Dialysis Data - Open-label Extension Period	Open-label Safety Analysis Set
16.2.5.4	Dialysis Type Adjustment - Open-label Extension Period	Open-label Safety Analysis Set
16.2.6.1	5-D Itch Scale - Open-label Extension Period	Open-label Safety Analysis Set
16.2.6.2	Skindex-10 Scale - Open-label Extension Period	Open-label Safety Analysis Set
16.2.7.1	All Adverse Events - Open-label Extension Period	Open-label Safety Analysis Set
16.2.7.2	Special Situations - Open-label Extension Period	Open-label Safety Analysis Set
16.2.7.3	Adverse Events Starting in the Double-Blind Period and Leading to Study Drug Discontinuation, Early Study Termination or Death in the Open-label Extension Period	Open-label Safety Analysis Set

	Titles	Population
16.2.8.1	Clinical Laboratory Results: Haematology - Open-label Extension Period	Open-label Safety Analysis Set
16.2.8.2	Clinical Laboratory Results: Serum Chemistry - Open-label Extension Period	Open-label Safety Analysis Set
16.2.8.3	Pregnancy Test Results (Females Only) - Open-label Extension Period	Open-label Safety Analysis Set
16.2.8.4	Comments of Clinical Laboratory Results - Open-label Extension Period	Open-label Safety Analysis Set
16.2.9.1	12-lead Electrocardiogram Results: Quantitative Assessment - Open-label Extension Period	Open-label Safety Analysis Set
16.2.9.2	12-lead Electrocardiogram Results: Qualitative assessment - Open-label Extension Period	Open-label Safety Analysis Set
16.2.9.3	Vital Signs - Open-label Extension Period	Open-label Safety Analysis Set

